TFTs is bolstered by our prior work examining post-TFT treatment needs (Section 2A.3.1). The overall objectives of the therapist-assisted self-management program are to increase Veterans' self-efficacy for managing their PTSD, enable the maintenance or building upon gains made in TFT (e.g. formalize the expectation for continued practice of TFT skills and provide structure for the ongoing use of skills), and encourage engagement in meaningful activities. The program's components, the element of effective SM

programs
addressed by each
component, and the
specific goals
associated with the
components are
outlined in Table 2
(strategies that will
be employed within
each component
are expanded upon
in the detailed
outline of the
intervention

Table 3. Self-Management Intervention & Assessment Schedule

	Weeks Since Final TFT Session												
Self-Management Sessions	0	1	2	3	4	5	6	7	8	9	10	11	12
In-person session	Χ				Χ								
Phone check in			Χ										
Phone session											Х		
Assessment Schedule													
Baseline survey	Χ												
Follow-up survey													Х
Follow-up interview													Х

included in the Appendix). TFT therapists will assist Veterans with tailoring their plan to reflect their goals,

strengths, and the TFT completed (*PE and CPT modules will be available for components that require TFT-specific content; e.g. continued practice of TFT skills*). The draft program proposes four planned therapist contacts over the ten weeks following TFT completion (Table 3). Specifically, TFT therapists will meet with Veterans in person or through V-tel at the conclusion of TFT (SM intervention introduced during an expanded final TFT session), by phone for a brief check in two weeks after TFT completion, in person or through V-tel approximately four weeks after TFT completion, and by phone ten weeks after TFT completion. Therapists will also be available for additional contact as needed by Veterans; however, as *Veterans gradually develop greater self-efficacy in managing their PTSD symptoms, their need for therapist contact should decrease. Intervention development and refinement is ongoing and will continue until immediately prior to the Aim 2 therapist training.*

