Data Collection. Data will be collected via a survey assessment, semi-structured qualitative interview, and administrative data. The outcomes of interest for Aims 2 & 3, the source from which the data will be drawn, and the specific survey measure (as applicable) are presented in Table 4. Participants will complete a survey assessment immediately before their final TFT session (baseline) and two weeks after their final SM program contact (follow-up; three months after final TFT session, see Table 3). The baseline survey will be administered in person; the follow-up survey will be administered via mail using a modified Dillman protocol frequently used by Drs. [name] and [name].⁵³ Participants who complete and return a survey will receive \$20 as compensation. Veterans will also complete a 45-60 minute semi-structured interview two weeks after the final SM therapist contact (follow-up). The interviews will follow the methodology described in Aim 1, with the exception that interviews will be conducted via telephone. As with Aim 1, the interviews will be conceptually informed by the "appropriateness" domain of Levesque et al.'s Patient-Centered Access to Health Care

Domain	Source	Survey Measure				
Acceptability						
Program Components & Structure	Survey; Interview	Credibility-Expectancy Scale*54; Client Satisfaction Scale**55				
Materials	Interview	N/A				
Feasibility						
Program Retention	Administrative; Interview	N/A				
Intervention Fidelity	Administrative	N/A				
Screening Approach	Administrative	N/A				
Recruitment Approach	Administrative	N/A				
Assessment Process	Survey; Interview	All Survey Measures				
Self-Efficacy Related to PTSD Self- Management	Survey; Interview	Personal Control Subscale of the Illness Perception Questionnaire Revised ⁵⁶				
Outcomes Associated with Improved Self- Management						
Symptomology (PTSD and Depression)	Survey; Interview	PTSD Checklist ⁵⁷ ; Patient Health Questionnaire-9 ⁵⁸				
Perceived Mental Health Functioning	Survey; Interview	Current Mental Health subscale o the Recovery Orientation Scale ⁵⁵				
Physical and Mental Health Functioning	Survey; Interview	Short Form Survey ⁶⁰				
Quality of Life	Survey; Interview	World Health Organization Qualit of life - BREF ⁶¹				
Community Engagement	Survey; Interview	Military to Civilian Questionnaire				
Psychosocial Functioning	Survey; Interview	Brief Inventory of Psychosocial Functioning				

* Baseline survey only; ** Follow-up survey only

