Data Analysis. To assess the acceptability of the treatment program, we will calculate the percentage of participants who report neutral or better treatment credibility and expectancy on the Credibility-Expectancy scale and examine the distribution of scores on the Client Satisfaction Scale. We will triangulate these quantitative data with qualitative themes related to acceptability (qualitative data will be analyzed using the same methodology as described in Aim 1 Data Analysis); specifically, we will create a matrix with themes that emerge from the interviews regarding the programs' acceptability stratified by Veterans' quantitative Credibility-Expectancy and Satisfaction scores. Qualitative themes regarding the feasibility domain of program retention will be triangulated with administrative data regarding session attendance; a matrix presenting themes associated with high, medium, and low attendance (tertiles) will be produced by [name]. Descriptive statistics and graphical representations depicting intervention fidelity, screening, and retention will be generated. To assess the feasibility of the assessment approach, we will calculate rates of survey non-response and item missingness. We will also create a matrix summarizing themes related to the assessment process. Finally, we will calculate and graphically display the direction and magnitude of change from baseline

to follow-up for self-efficacy and outcomes associated with improved SM; we will also calculate the percentage of participants who improved, worsened, and experienced no change for each of these measures. These quantitative data will be triangulated with qualitative themes regarding self-efficacy and other program-related outcomes; themes and exemplary quotations will be presented in a matrix stratified by self-reported change (improved, worsened, no change) on the survey measures. We will also calculate descriptive statistics and pre-to-post treatment effect sizes for the sample.

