Aim 2. We will enroll 12 Veterans that seek care at either the Minneapolis VAHCS or Northwest Metro VA Clinic (Ramsey, MN), to participate in the post-TFT therapist-assisted self-management intervention. Veterans will be asked to participate in the self-management intervention, complete a brief survey at baseline (immediately prior to the first self-management session) and follow-up (12 weeks later), and participate in a 45minute semi-structured interview at the follow-up time point. While follow-up procedures are planned to be completed 12 weeks after a participant's first self-management session, there can be unforeseen scheduling and logistical conflicts that may push this timeline back. Provider and veteran can handle these circumstances on an individual basis and adjust the timeline as seen fit. Follow-up procedures should be completed with the goal of 12 weeks after the first self-management session but can be completed up to 16 weeks after the first self-management session if unable to stick to the original outlined study schedule. Veterans will be eligible to participate if they (a) are about to complete a course of individually-delivered TFT (enrollment will occur one to three weeks prior the final session or immediately before the final session) with a provider trained to deliver the self-management intervention, (b) experienced a clinically meaningful reduction in PTSD symptomology (PCL decrease of at least 10 points) from pre-TFT to the time of the enrollment, (c) at the time of enrollment are not planning to initiate another active course of psychotherapy for PTSD in the following three months, (d) are willing to participate in a self-management intervention, and (e) can provide informed consent. Veterans will be excluded if they have suicidal or homicidal ideation that in the opinion of their TFT therapist needs to be the focus of treatment. We will use a combination of provider referrals and administrative data to identify potential participants. We will also access VHA administrative data for surveyed Veterans in order to collect contact information, demographic characteristics, and mental health service utilization information.

2. Data Sources

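### The screen for planned PTSD psychotherapy runs three months from enrollment, so it ends before follow-up for Veterans enrolled two to three weeks early or followed up at about week 14 or later

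*Combined protocol and SAP*

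**What the plan says.** Criterion (c) (Human Subjects, section 1, Aim 2) requires that Veterans "at the time of enrollment are not planning to initiate another active course of psychotherapy for PTSD in the following three months". The same paragraph sets the time of entry: "enrollment will occur one to three weeks prior the final session or immediately before the final session". Section 2A.4.2 and the Veteran recruitment and consent text make consent one to three weeks ahead the standard route, with same-day consent as the fallback.

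The outcome clock starts later. In section 2A.4.1 the first self-management (SM) session is the last TFT session: "SM intervention introduced during an expanded final TFT session". Section 2A.4.2, Data Collection, sets both survey points: "Participants will complete a survey assessment immediately before their final TFT session (baseline) and two weeks after their final SM program contact". The last planned SM contact is "by phone ten weeks after TFT completion", and follow-up is described as "follow-up; three months after final TFT session, see Table 3". The Aim 2 paragraph also allows delay: follow-up "can be completed up to 16 weeks after the first self-management session if unable to stick to the original outlined study schedule".

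Under Data Analysis (section 2A.4.2) the investigators will "calculate and graphically display the direction and magnitude of change from baseline" to follow-up. They will also classify each Veteran as better, worse or unchanged, stratify the qualitative themes by that class, and compute pre-to-post effect sizes. The Aim 2 paragraph provides for collecting data on mental health service use. Neither the list of administrative data to extract nor the analysis text uses those data to find or handle a new course of psychotherapy.

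**The concern.** Criterion (c) is the only eligibility rule that deals with further PTSD psychotherapy, and its evident purpose is to keep a planned new course out of the step-down period being measured. Its window starts before the outcome window, has a fixed length, and is not tied to the follow-up date. A Veteran can therefore meet it while already planning a course that begins before the follow-up survey.

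The trial has one arm, so no comparison group shares that influence. Change in PTSD symptoms, depression, functioning or self-efficacy for such a Veteran would mix the SM program with the start of other active treatment. One Veteran is 1/12 = 8.3% of the sample. A change of class for one Veteran moves a reported percentage by that amount and moves the Veteran's themes to another column of the matrix. The results are meant to support an application for a randomized trial.

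**Working it through.** **Inputs**
- Length of screen: three months from enrollment (criterion (c)). Two readings are used: 12 weeks, because section 2A.4.2 and Table 3 equate three months with week 12; and three calendar months, which is 89 to 92 days (about 13 weeks).
- Enrollment lead before week 0: 0, 1, 2 or 3 weeks (Aim 2 paragraph), taking enrollment as the time of consent.
- Week 0: final TFT session, first SM session and baseline survey (sections 2A.4.1 and 2A.4.2).
- Follow-up: week 12 planned, week 16 at latest.

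**The plan's own figure.** Last SM contact at week 10 + 2 weeks = week 12. This agrees with Table 3 and with the 12 weeks in the Aim 2 paragraph.

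**Formulas**
- Enrollment to follow-up (weeks) = lead + follow-up week.
- Shortfall, 12-week reading = lead + follow-up week − 12.
- Shortfall, calendar reading (days) = 7 × (lead + follow-up week) − 92, to the same product − 89. A negative value means covered.

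| Lead (weeks) | Follow-up week | Enrollment to follow-up (weeks) | Shortfall, 12-week reading (weeks) | Shortfall, calendar reading (days) |
|---|---|---|---|---|
| 0 | 12 | 12 | 0 | −8 to −5 (covered) |
| 1 | 12 | 13 | 1 | −1 to 2 (tie) |
| 2 | 12 | 14 | 2 | 6 to 9 |
| 3 | 12 | 15 | 3 | 13 to 16 |
| 0 | 13 | 13 | 1 | −1 to 2 (tie) |
| 0 | 14 | 14 | 2 | 6 to 9 |
| 0 | 16 | 16 | 4 | 20 to 23 |
| 1 | 16 | 17 | 5 | 27 to 30 |
| 2 | 16 | 18 | 6 | 34 to 37 |
| 3 | 16 | 19 | 7 | 41 to 44 |

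**Reading the table.** Under both readings the screen ends early for a lead of two or three weeks, even with on-time follow-up: 6 days (about 1 week) to 3 weeks short. It also ends early for every lead once follow-up reaches about week 14. At week 16 the shortfall runs from 20 days (about 3 weeks) to 7 weeks.

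**Example.** A Veteran enrolls three weeks early and already plans a new course for week 11. That is 3 + 11 = 14 weeks, or 98 days, after enrollment. This exceeds both 12 weeks and 92 days, so criterion (c) is met under either reading. The course would have run for 1 week at a week-12 follow-up and for 5 weeks at week 16.

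**Span needed.** Counted from enrollment, the screen would have to last 3 + 12 = 15 weeks to reach an on-time follow-up for the earliest enrollee, and 3 + 16 = 19 weeks to reach the latest one. Counted from the first SM session, the spans are 12 and 16 weeks.

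**The case against.** The route to harm is narrow. It needs a Veteran who has improved on TFT and is willing to try self-management, yet already plans another active course some 12 to 15 weeks ahead (up to 19 with late follow-up) and not sooner. The protocol reports that over 90% of TFT completers see a need for more mental health care, but that is not a rate of planned PTSD courses. A course begun near the end of the interval has little time to act. Late follow-up is provided for as an exception. Aim 3 is exploratory and descriptive, with no hypothesis test. The service-use data and the individual interviews could bring an affected case to light among 12 Veterans.

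All of this stands and limits the size of the point. It does not align the two windows, and the plan does not say that the service-use data will be used for this purpose.

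Three stronger readings are tempting, and the documents do not support them.
- A reader might infer that the screen fails for every early enrollee and every late follow-up. That holds only if three months means exactly 12 weeks. By calendar months, two of the combinations tabulated above are ties.
- A reader might infer that about six sessions of new therapy could fit in. That needs the earliest enrollment, the latest follow-up, a start as soon as the screen lapses, and weekly visits. The six PE or eight CPT sessions in section 2A.4.2 are a trigger for chart review. They are not evidence that so many sessions would shift outcomes.
- A reader might infer that an affected Veteran's change is uninterpretable. Partly confounded is the most that can be said.

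**Conclusion.** The mismatch is real and minor. As worded, criterion (c) can admit a Veteran who already plans a course inside the measured interval. This is clear for enrollment two to three weeks early and for any follow-up at about week 14 or later. It rests on enrollment being the time of consent, on the first SM session falling at week 0, and on three months meaning 12 to 13 weeks.

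The effect is confined to the Aim 3 change results of whichever Veterans are affected. The documents give no figure from which their number, or the direction or size of any bias, could be derived. Courses that were not planned at enrollment are a separate matter, which no screen on stated plans can settle.

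**What to change.** 1. In criterion (c), replace the three-month limit with a single date tied to the outcome window: 16 weeks after the first SM session, the latest permitted follow-up. One date leaves the screener in no doubt, and the result no longer depends on how three months is read.
2. Ask the same question again at the baseline survey, to catch plans that changed after early consent.
3. In Data Analysis, state that the service-use data will be used to flag any Veteran who began a new course of PTSD psychotherapy before follow-up. Show the change results with and without flagged Veterans. VHA records will not show care received elsewhere.

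The cost is one line in the criteria, one item on the screening form and one sentence in the analysis text. Some more Veterans may be ineligible, including some whose planned course would have started after an on-time week-12 follow-up. The protocol's estimate of 64 eligible Veterans states no allowance for criterion (c), but against 12 places it leaves room. The criterion concerns stated plans only and restricts no Veteran's care.
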